### **10.7.3. Suicidality and Depression**

The number and percentage of subjects that endorse suicidal ideation and suicide attempt at any time during the study will be presented based on the responses to the Columbia Suicide Severity Rating Scale (CSSR-S). For HAM-D17 scores, the mean, SD, change from Day -1, median, and range of all values at each time point will be presented in a summary table. The number and percentages of subjects with scores greater than 7, that is considered to be indicative of clinical depression will be presented for all timepoints.

### **9.7.4 Clinical Laboratory**

Descriptive statistics will be generated for all tests performed at screening and at each clinic visit. If a laboratory analysis is repeated, the last measurement performed prior to the clinic visit will be used in the summary statistics for that clinic visit. If an unscheduled clinical laboratory visit occurs prior to a scheduled visit that is missed due to dropout, then the unscheduled visit will be used in the summary statistics for the missed scheduled clinical visit. If an unscheduled clinical laboratory visit occurs between two scheduled clinical visits, then the data from the unscheduled visit will only be presented in the listings and not in summary statistics. In addition, at each post-randomization clinic visit descriptive statistics for change from baseline will be generated for clinical chemistry and hematology tests. Laboratory values will be plotted as mean  $\pm$  standard error over time. All laboratory measurements will be presented in the listings including an assessment if the laboratory value is considered within normal limits or is not clinically significant or is clinically significant.

The number and percentage of positive urine drug tests and pregnancy tests for screening visits and all treatment and follow-up visits will be tabulated. Results of all urine drug tests and pregnancy tests will be presented in the listings. The percentage of subjects with a positive urine drug test at any time post start of treatment will also be presented by test type and treatment group.

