### 9.2 Safety

Adverse Events and Serious Adverse Events: AE data will be listed individually and summarized by Medical Dictionary for Regulatory Activities (MedDRA) body system and preferred terms within a body system by severity and relationship to the investigational product. Serious and/or unexpected AEs will also be discussed on a case-by-case basis. For the tabulation of the AEs by

preferred term, a subject will be counted only once under each preferred term by maximum severity and closest relationship to the investigational product.

Clinical Laboratory Data (chemistry, hematology, coagulation, infectious serology, urine drugs): The mean, SD, mean change where applicable, median, and range of all values for each test at each time point will be presented in a summary table. Values will be compared to normal according to CTC v 5.0. Individual abnormal values will be presented and discussed.

Vital signs including blood pressure and heart rate will be presented as summary statistics and change from baseline. Values will be compared to normal according to CTC v 5.0. Individual abnormal values will be presented and discussed.

Concomitant medications will be presented in a listing including the verbatim term, dose, frequency, start and stop dates, and indication.

Suicidality and depression: For the Columbia Suicide Severity Rating Scale, the number and percentage of subjects that endorse suicidal ideation and suicide attempt will be presented. For HAM-D17 scores, the mean, SD, change from screening, median, and range of all values at each time point will be presented in a summary table. Scores of 0 to 7 are considered to not be indicative of clinical depression.

Demographics and other entrance examinations: Summaries of the subject demographics, blood alcohol tests, and naloxone challenge tests will be presented.

By-subject listings will be provided for clinical laboratory, vital signs, demographic data, medical history, physical examination results, vital signs, blood alcohol tests, naloxone challenge tests, concomitant medications, depression/suicidality.

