## 10.6 Severity Assessment

All AEs will be assessed for severity by the investigator. Inherent in this assessment is the medical and clinical consideration of all information surrounding the event including any medical intervention required. Each event will be assigned one of the following categories: mild, moderate, severe, or life-threatening. Clinically Significant labs should be reported as AEs. Abnormalities in vital signs will be reviewed by the Investigator staff. The Investigator will have the authority to determine if any action needs to be taken with the abnormal vital signs and/or if the abnormality should be considered an AE. All laboratory abnormalities and vital sign abnormalities graded in accordance with CTC AE criteria will be considered when implementing progression rules (Section 7.8.1).

Any grade 4 (life-threatening) AE must be reported as an SAE.

The eCRF for AEs will reflect only the highest severity for continuous days an event occurred.

Mild	Grade 1	Does not interfere with routine activities Minimal level of discomfort
Moderate	Grade 2	Interferes with routine activities Moderate level of discomfort
Severe	Grade 3	Unable to perform routine activities Significant level of discomfort
Potentially life-threatening	Grade 4	Hospitalization or ER visit for potentially life-threatening event

FDA guidelines for toxicity will be followed; however, if a subject is evaluated in an emergency room for nonlife threatening illness or symptoms (ie, visits emergency department on weekend for mild problems because the physician's office is closed), the information from that visit will be reviewed and severity of the adverse event will be assessed according to the subject's clinical signs and symptoms.

As defined by the ICH guideline for GCP, the term "severe" is often used to describe intensity (severity) of a specific event (as in mild, moderate, or severe myocardial infarction); the event itself however, may be of relatively minor medical significance (such as severe headache). This is **not** the same as "serious", which is based on subject/event outcome or action criteria usually associated with events that pose a threat to a subject's life or functioning. Seriousness (not severity) serves as a guide for defining regulatory reporting obligations.

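### A transient laboratory abnormality can be missing from the SAP's lab summary tables, and the CTCAE comparison planned for labs in the protocol is not carried out

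*SAP*

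**What the plan says.** SAP 9.7.4 (Clinical Laboratory) has three rules for choosing values:

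- Repeated test: "the last measurement performed prior to the clinic visit will be used in the summary statistics for that clinic visit". The rule covers any repeat and gives no reason for repeating.
- Unscheduled draw before a scheduled visit that is missed because of dropout: "then the unscheduled visit will be used in the summary statistics for the missed scheduled clinical visit".
- Unscheduled draw between two scheduled visits: "then the data from the unscheduled visit will only be presented in the listings and not in summary statistics".

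The same section keeps every result in the listings: "All laboratory measurements will be presented in the listings including an assessment if the laboratory value is considered within normal limits".

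The shells for Tables 25 (chemistry) and 26 (hematology) give N, mean (SD) and minimum–maximum by visit, and the same for change from baseline. The SAP's list of tables has no laboratory table by CTCAE grade, no shift table and no worst post-baseline value.

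Protocol 9.2 says of laboratory data: "Values will be compared to normal according to CTC v 5.0". It also requires individual abnormal values to be presented and discussed. Protocol 10.6 adds: "Clinically Significant labs should be reported as AEs", and "All laboratory abnormalities and vital sign abnormalities graded in accordance with CTC AE criteria will be considered when implementing progression rules". For vital signs, the SAP plans counts of subjects at CTCAE grade 2 or higher by treatment group. It plans none for labs.

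**The concern.** Protocol 4.4 lists hepatic enzyme abnormality among the adverse events of the marketed naltrexone injection, and protocol 5.2 names hepatotoxicity and reticulocytes as follow-up targets. With about six active subjects per dose level, one value can set the group maximum and move the mean.

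Between scheduled lab visits, an unscheduled draw may be the only one that catches a short-lived rise, and the SAP leaves that result out of the summaries. A repeat may displace an earlier valid result. Nothing in the planned lab tables brings either value back. A reader who relies on Tables 25 and 26 could then see an unremarkable profile for a subject who had a real, brief abnormality. The CTC comparison planned in the protocol would show it, but the SAP does not implement that comparison for labs.

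**Working it through.** The plan states no figure that could be reproduced: it tests no hypotheses, and six per dose level is justified by convention. The check is therefore a reading of the rules, followed by an illustration on assumed inputs.

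**Step 1. Gaps between scheduled labs.** The protocol timetable places post-dose chemistry and hematology at 72 hours and Weeks 4, 8 and 12. On the nominal times in SAP Table 9, 72 hours is week 0.429, so the first gap is 4.000 − 0.429 = 3.571 weeks (25 days). The next two are 28 days each. With the ±3-day visit window, the gap from Week 4 to Week 8 can reach 28 + 3 + 3 = 34 days.

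**Step 2. Where each kind of result goes.**

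| Result | Tables 25–26 | Listings | AE tables |
|---|---|---|---|
| Scheduled, not repeated | Yes | Yes | If clinically significant |
| Repeated before a visit, earlier value | No | Yes | If clinically significant |
| Unscheduled, scheduled visit missed through dropout | Yes | Yes | If clinically significant |
| Unscheduled, between two scheduled visits | No | Yes | If clinically significant |
| Retest drawn after a visit because of that visit's result | Unclear | Yes | If clinically significant |

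The last row is unclear because the repeat rule takes the last value before the clinic visit. Read literally, a later retest is an unscheduled result between visits, so it is only listed and the visit value stands. Read loosely, the retest replaces the visit value. Two programmers could produce different tables.

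**Step 3. Protocol against SAP.** Protocol 9.2 plans a CTC v5.0 comparison for both labs and vital signs. The SAP plans CTCAE grade counts for vital signs only. This gap does not depend on how the repeat rule is read.

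**Step 4. Illustration, n = 6 (assumed values, in multiples of the upper limit of normal, ULN).** Five subjects are at 0.6 and one is at 5, with a repeat at 2 that counts as the visit value.

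- First value kept: mean = (5 × 0.6 + 5)/6 = 8/6 = 1.33; maximum 5.
- Repeat kept: mean = (5 × 0.6 + 2)/6 = 5/6 = 0.83; maximum 2.

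**Step 5. Selective repeats, no drug effect (assumed).** Let X be the first value and R the repeat, both log-normal with the same subject mean. Only values above the limit U are repeated, and the repeat is kept. The share above the limit then falls from P(X > U) to P(X > U and R > U), a bivariate normal probability with correlation ρ = between-subject variance/total variance.

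| Log-SD between / within | Limit | ρ | First value | After selective repeat |
|---|---|---|---|---|
| 0.30 / 0.10 | 97.5th percentile | 0.900 | 2.5% | 1.5% |
| 0.30 / 0.20 | 97.5th percentile | 0.692 | 2.5% | 0.8% |
| 0.30 / 0.30 | 97.5th percentile | 0.500 | 2.5% | 0.5% |
| 0.35 / 0.25 | median 0.6 × ULN | 0.662 | 11.7% | 5.4% |
| 0.45 / 0.35 | median 0.6 × ULN | 0.623 | 18.5% | 9.2% |

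If everyone is repeated regardless of result, the share does not change. For six subjects, the first three rows mean 6 × 0.025 = 0.15 expected exceedances, falling to between 6 × 0.005 = 0.03 and 6 × 0.015 = 0.09.

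**The case against.** A reader might infer that the safety tables as a whole are biased towards normal and that unscheduled results are kept out of every summary. The documents do not support that.

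- An unscheduled result is summarised when the scheduled visit is missed through dropout.
- The repeat rule is not tied to abnormal results, and the documents do not say when tests are repeated. On the literal reading, a retest after a visit cannot displace the abnormal visit value.
- Clinically significant labs become adverse events and enter those tables. Every result is listed, and protocol 9.2 requires abnormal values to be discussed individually. With eight subjects per cohort, reading listings is realistic.
- It is also tempting to say that dose escalation was put at risk. The progression committee grades events itself, and nothing says that it relies on Tables 25 and 26. SAP section 3 records that the SAP was finalised after the decision not to go beyond dose level 2, so its wording cannot affect escalation.
- The magnitudes are invented inputs. The 11.7% and 18.5% starting shares are high for volunteers selected for normal laboratories. Tables 25 and 26 do not report a share above the limit, and a pure-noise model shows chance exceedances disappearing, not a drug effect being hidden.

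All of this stands, and it limits the point to the laboratory summaries. It does not remove the point. Entry as an adverse event rests on a judgement of clinical significance, and a listing is not the grade comparison planned in the protocol.

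**Conclusion.** The point holds for the laboratory summary tables. Two features follow from the text alone: unscheduled results between scheduled visits do not enter Tables 25 and 26, and no laboratory table by CTCAE grade is planned although protocol 9.2 calls for the comparison. A brief abnormality can therefore be absent from the lab summaries while remaining in the listings and possibly in the adverse event tables.

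Any bias towards normal in the by-visit summaries is conditional. It needs repeats that are done selectively after high values and that count as the visit value. The documents establish neither. The size is not known from the documents. The n = 6 case shows only that one replaced value can matter at this sample size. This is a reporting gap that should be closed, not an error that invalidates the safety analysis.

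**What to change.** 1. Add one table each for chemistry and hematology showing worst post-implant CTCAE v5.0 grade against baseline grade, by treatment group, using all scheduled, repeat and unscheduled results. Define baseline as the last value before implantation; on the protocol timetable that is Screening.
2. Keep the by-visit summaries, and add one sentence to SAP 9.7.4 stating which value is used when a retest follows a visit result, so that a valid abnormal result is not silently replaced. Using the first valid sample is one workable convention among several; what matters is that the choice is written down.

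The cost is two extra tables and one sentence of SAP text. No new data are needed, because every result is already collected and listed.

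While the shells are open, note a separate matter: the visits in Tables 25 and 26 stop at Week 8, although the timetable schedules these labs at Week 12 as well.

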### Progression procedures and rules:

SARs: If 1 subject at a dose level experiences an SAE that is decided after breaking the code to be an SAR, further entry into that dose level will be at least temporarily stopped. Further accrual to that dose level may carefully proceed with more frequent adverse event monitoring and reporting. The timing of additional AE monitoring will depend on the time the SAR occurred. The additional event data, whether adverse or not, will be reported and considered by the PI and representative of the Sponsor within 7 days, with an SAE reported within 3 days. If a 2nd subject experiences an SAR, accrual to that dose level will stop and accrual to the study will stop. If not more than 1 of the 6 Biopin subjects at that dose-level experience an SAR, 8 further subjects (randomized 6 Biopin vs 2 placebo) will be entered into that dose level. Progression to the next dose-level will occur if none of the extra 6 Biopin subjects experience an SAR or a grade 4 AR.

Grade 3-4 Adverse Reactions: If  $\geq 1$  of the 6 BIOTIN 6 subjects at a dose level experiences a grade 3-4 adverse event evaluated in accordance with the National Cancer Institute Common Toxicity Criteria (NCI-CTC) (Ver 5.0) that is decided after breaking the code to be an adverse reaction, escalation to the next level of drug will be at least temporarily stopped. Progression to the next dose level will not occur unless 8 more subjects (randomized 6 Biopin vs 2 placebo) have been entered into the present dose level without any grade 3-4 adverse reactions.

Grade 2 Adverse Reactions: If  $\geq 3$  of the 6 BIOPIN 6 subjects at a dose level experience a grade 2 adverse event determined after breaking the code to be an adverse reaction, escalation to the next level of drug will be at least temporarily stopped. Progression to the next dose level will not occur unless more subjects have been entered into the present dose level with no more than one grade 2 adverse reactions.

If 0-2 of the subjects at a dose level experiences a grade 2 adverse event, escalation to the next dose level will proceed.

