### **9.6.3 Vital Signs**

Vital signs will be presented as summary statistics and change from baseline. Values will be graded in accordance with the common criteria for adverse events (CTC-AE) version 5. The number and percentage of subjects with a vital sign measurements meeting grade 2 or greater criteria will be summarized by treatment group and CTC-AE grade. The percentage of ECG results considered abnormal and clinically significant will be presented as numbers and percentages for each timepoint. Vital signs and ECG results for all visits will be presented in the listings.

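### SAP 9.7.4 omits, without declaring it, the CTC v5.0 comparison of laboratory values promised in protocol 9.2, so graded values judged not clinically significant are counted in no visible table

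*SAP*

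**What the plan says.** Protocol 9.2 asks for three things for clinical laboratory data. The first is a summary table with the "mean, SD, mean change where applicable, median, and range of all values for each test at each time point". The second is a comparison: "Values will be compared to normal according to CTC v 5.0". The third is presentation and discussion of individual abnormal values. The comparison sentence is repeated word for word for vital signs.

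Protocol 10.6 keeps two judgments apart. One concerns reporting: "Clinically Significant labs should be reported as AEs". The other concerns dose escalation and has no clinical-significance filter: "All laboratory abnormalities and vital sign abnormalities graded in accordance with CTC AE criteria will be considered when implementing progression rules".

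SAP 9.6.3 carries the comparison through for vital signs: "Values will be graded in accordance with the common criteria for adverse events (CTC-AE) version 5". It then counts subjects at grade 2 or higher, by treatment group and grade.

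SAP 9.7.4 never mentions CTC. It starts with "Descriptive statistics will be generated for all tests performed at screening and at each clinic visit", adds change from baseline and plots, and ends with the listing: "All laboratory measurements will be presented in the listings including an assessment if the laboratory value is considered within normal limits", not clinically significant, or clinically significant.

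SAP section 2 presents the document as holding every planned analysis. SAP section 3 declares one change, the decision not to proceed to the third dose level.

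**The concern.** The protocol gives the same commitment for two data types, and the SAP keeps it for one. The flag in 9.7.4 is an investigator's judgment of clinical significance, not a grade on an external scale, so it does not replace the CTC comparison.

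This matters for this drug. Protocol 4.4 names hepatic enzyme abnormality as a naltrexone harm, and protocol 5.2 names hepatotoxicity and reticulocytes as follow-up targets. Exclusion criterion 1 admits subjects whose liver tests lie up to 25% outside the normal range, so a post-implant grade can only be interpreted next to the pre-implant grade. A first-in-human safety report should let the reader see how many subjects had a graded rise, including rises the investigator considered unimportant.

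**Working it through.** **1. Where a graded laboratory value can appear.** I followed each kind of value through the visible outputs.

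| Laboratory value | Route under the plan | Counted in a visible table? |
|---|---|---|
| Clinically significant | Reported as an AE (protocol 10.6) | Yes: Tables 13-16 and 18 |
| CTC-graded, judged not clinically significant | Listing flag; contributes to mean, SD and min-max | No |

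For the first row, protocol 7.8.1 and 10.6 leave open which severity scale applies: 7.8.1 uses NCI-CTC v5.0, while 10.6 gives a scale based on interference with activities. For the second row, none of the 30 listed tables or 5 listed figures counts laboratory grades, shifts or abnormal values. The CTC comparison is promised for 2 data types and specified in the SAP text for 1.

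**2. Whether the planned statistics could give the count.** Take six values per dose level and an assumed upper limit of 40. The documents give no limit; rescaling all values gives the same result for any other.

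- Set A: 20, 22, 40, 40, 40, 60. Sum 222, mean 222/6 = 37.0. Squared deviations 289 + 225 + 9 + 9 + 9 + 529 = 1070. SD = √(1070/5) = 14.63. Above 40: 1 of 6 = 16.7%.
- Set B: 20, 25, 31, 43, 43, 60. Sum 222, mean 37.0. Squared deviations 289 + 144 + 36 + 36 + 36 + 529 = 1070. SD = 14.63. Above 40: 3 of 6 = 50.0%.

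N, mean, SD and min-max (20-60) are identical, and these are the rows in Tables 25 and 26. The medians differ (40 and 37), so I repeated the check with the median also held equal.

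- Set C: 20, 25, 25, 40, 40, 60. Mean 210/6 = 35.0, median 32.5. Squared deviations 225 + 100 + 100 + 25 + 25 + 625 = 1100. SD = √(1100/5) = 14.83. Above 40: 1.
- Set D: 20, 22, 31, 34, 43, 60. Mean 35.0, median 32.5. Squared deviations 225 + 169 + 16 + 1 + 64 + 625 = 1100. SD = 14.83. Above 40: 2.

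Restoring the median narrows the ambiguity but does not remove it. The maximum is also not fully reliable. Under 9.7.4 an unscheduled value between two scheduled visits goes only to the listings, and a repeated test is represented by its last measurement, so a peak can be missing from min-max.

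**3. Weight of one subject.** Active: 1/6 = 16.7% of a dose level. Placebo: 2 cohorts × 2 = 4 pooled subjects, so 1/4 = 25%.

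**4. The Table 25 and 26 shells against the schedule.** I take Day 3 in the shells to be the 72-hour draw.

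| | Screening | Day -1 | 72 h | Week 4 | Week 8 | Week 12 |
|---|---|---|---|---|---|---|
| Scheduled (timetable, protocol 8.4) | yes | no | yes | yes | yes | yes |
| In shells | yes | yes | yes | yes | yes | no |

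Four of the five shell visits match the five scheduled draws. One shell visit (Day -1) has no scheduled chemistry or hematology draw, and one scheduled draw (Week 12) is missing. The median, required by protocol 9.2 and SAP 10.1, is also missing.

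**The case against.** The strongest reply is that this reads too much into silence. The SAP says it expands on the protocol, so the protocol sentence may still be in force. Protocol 9.2 promises a comparison, not a count table, and a grade column in a listing could deliver it. The listing shells are redacted and the section 11 safety-monitoring tables are not shown. That limit is real, which is why the point rests on the text of 9.7.4 and speaks only of visible tables. The missing grade rows prove little on their own, since Table 29 also lacks the rows that 9.6.3 plans for vital signs. But a plan that claims to contain all analyses, and specifies the CTC step in one section and a different step in the other, has departed from the protocol without saying so.

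Several narrower objections also stand. SAP 9.6.3 tabulates only grade 2 or higher, so the table proposed below is broader than that precedent; the comparison with the pre-implant grade is a recommendation, not a protocol requirement. The illustration counts values above a limit, not CTC grades, sets aside change from baseline, and places some values exactly at the limit. It shows that the summaries do not determine a count; it does not predict results. Reticulocytes are a named follow-up target and should not be left out of the remedy.

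The practical gap is modest: about 16 subjects (2 cohorts of 8), every value listed, and clinically significant values counted as AEs. The shell errors are a separate matter, and the governing text already requires what they omit.

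**Conclusion.** The concern holds. SAP 9.7.4 does not specify the CTC v5.0 comparison that protocol 9.2 promises for laboratory values, and SAP section 3 does not declare the omission. The consequence is limited but real: graded values judged not clinically significant have no visible count, in groups where one subject is 16.7% (active) or 25% (pooled placebo). Followed as drawn, the shells would also leave the Week 12 laboratory data, the draw at the end of exposure, out of the summary tables.

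This should be corrected. It does not affect the pharmacokinetic objective or escalation. The conclusion assumes that neither the redacted listing shells nor the unseen section 11 tables supply the grading; if they do, the defect is that 9.7.4 fails to describe it.

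**What to change.** - In SAP 9.7.4, state that post-implant chemistry and hematology values, including Week 12 and unscheduled values, will be graded by CTC-AE v5.0, as 9.6.3 does for vital signs.
- Add one table of n (%) of subjects by worst post-implant grade exceeding the pre-implant grade, by treatment group. Cover at least liver tests, creatinine, hemoglobin, WBC and platelets. Include reticulocytes as well; if CTC provides no grade for them, count values outside the normal range.
- Leave the 9.7.4 rule for unscheduled values in the visit summaries unchanged.
- In Tables 25 and 26, add Week 12 and the median and remove Day -1.
- If the sponsor prefers not to grade, declare the departure from protocol 9.2 in SAP section 3. The shell corrections are needed either way.

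The cost is one SAP sentence, one derived table and two shell corrections, all from data already collected. The small downside is an extra table that will display some asymptomatic graded values.

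### The SAP plans CTC grading for vital signs but not for laboratory values, and its repeat and unscheduled-visit rules let Tables 25-26 miss a subject's worst result

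*SAP*

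**What the plan says.** **Protocol.** Section 9.2 has the same instruction under clinical laboratory data and under vital signs: "Values will be compared to normal according to CTC v 5.0. Individual abnormal values will be presented and discussed". For laboratory tests it also asks for the range of all values at each time point. Section 10.6 says: "All laboratory abnormalities and vital sign abnormalities graded in accordance with CTC AE criteria will be considered when implementing progression rules (Section 7.8.1". It also says which results enter the adverse event record: "Clinically Significant labs should be reported as AEs".

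**SAP, vital signs.** Section 9.6.3 adopts CTC-AE version 5 and promises that the number and percentage of subjects with "vital sign measurements meeting grade 2 or greater criteria will be summarized by treatment group and CTC-AE grade".

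**SAP, laboratory.** Section 9.7.4 plans descriptive statistics at each clinic visit, change from baseline and mean plots. Every result goes into a listing, "including an assessment if the laboratory value is considered within normal limits or is not clinically significant or is clinically significant". No CTC grade is mentioned. If a test is repeated, "the last measurement performed prior to the clinic visit will be used in the summary statistics for that clinic visit". If an unscheduled result falls between two scheduled visits, "then the data from the unscheduled visit will only be presented in the listings and not in summary statistics". The one exception is an unscheduled result that stands in for a scheduled visit missed through dropout.

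**SAP, scope.** Section 2 describes the SAP as holding all planned analyses. Section 3 reports one change, the decision to stop after the second dose level.

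**The concern.** One protocol instruction covers two kinds of safety data, and the SAP turns it into a graded count for only one of them. The kind left out matters more for this drug. Protocol 4.4 names hepatic enzyme abnormalities and a modest fall in platelets among the effects of naltrexone, and Protocol 5.2 says subjects are followed for hepatotoxicity. Laboratory values are part of the secondary objective in both documents.

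A reader of the report will want to know how many subjects at each dose had a laboratory value of grade 2 or higher. The planned tables do not answer that. The summaries in Tables 25-26 are built visit by visit under rules that can pass over a subject's worst value. An out-of-range result is the kind most likely to be repeated or followed up off schedule, so the rules bear on the values of most interest.

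**Working it through.** The plan gives no figure on this point, so there is none to reproduce. The check sets the texts side by side and then shows with assumed values what the summary rules can do.

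**1. The two kinds of data compared**

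| | Vital signs | Laboratory values |
|---|---|---|
| Protocol 9.2 | compared with normal by CTC v5.0 | compared with normal by CTC v5.0 |
| Protocol 10.6 | CTC-graded abnormalities considered in progression | CTC-graded abnormalities considered in progression |
| SAP text | CTC-AE v5 grade; subjects at grade 2 or above counted by group and grade (9.6.3) | normal / not clinically significant / clinically significant, in the listing (9.7.4) |
| Reason for the difference (SAP section 3) | – | none given |

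The SAP itself read the 9.2 sentence as grading when it wrote the vital signs section, so the same reading for laboratory values is natural.

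**2. Unscheduled result between visits.** Assume six active subjects, with values as multiples of the upper limit of normal:
- Week 4: 0.6, 0.7, 0.5, 0.8, 0.6, 0.9. Mean 4.1/6 = 0.68, maximum 0.9.
- Week 8: 0.6, 0.7, 0.6, 0.8, 0.6, 0.9. Mean 4.2/6 = 0.70, maximum 0.9.

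Suppose one subject reaches 6.0 at an unscheduled visit between the two. That value is listed only. Both table columns stay as above, with a maximum of 0.9.

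**3. Repeated test.** Keep five of the Week 4 values (0.6, 0.7, 0.5, 0.8, 0.6; sum 3.2). The sixth subject has a first result of 6.0 and a repeat of 1.2 before the visit.
- First result used: mean (3.2 + 6.0)/6 = 1.53, maximum 6.0.
- Last result used, as 9.7.4 states: mean (3.2 + 1.2)/6 = 0.73, maximum 1.2.

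A worst-grade table drawing on all post-dose values would include the 6.0 in either case.

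**4. Scale.** One of six subjects is 1/6 = 16.7%. The exact 95% interval (Clopper-Pearson: the 2.5% point of Beta(1, 6) and the 97.5% point of Beta(2, 5)) is 0.4% to 64.1%. At this sample size one subject changes the description of a dose level.

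**5. Do the adverse event tables fill the gap?** In part. A laboratory result becomes an adverse event if it is judged clinically significant. Its severity is then assigned by the investigator under 10.6, where the printed scale turns on interference with daily activity and discomfort. A CTC laboratory grade is a different measure, so the two could differ for a result without symptoms.

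**6. Week 12.** Both timetables schedule chemistry and hematology at Week 12. The visit lines in the shells of Tables 25 and 26 end at Week 8, although the text of 9.7.4 covers each clinic visit.

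**The case against.** The strongest reply is that the protocol requires no count of subjects by laboratory grade. Section 9.2 asks for comparison with normal and for discussion of individual abnormal values. The word graded appears in 10.6, in support of the progression rules. With 12 active subjects, a full listing and case-by-case discussion could satisfy 9.2. This stands: the point is a gap in what the SAP plans, and no mandated table has been dropped.

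The shells are also weak evidence. None of Tables 1-30 shows a laboratory grade, but Table 29 shows no vital sign grade either, although the SAP text plans one. The listing shells are redacted and may hold a grade column. SAP section 11 announces tables for the Safety Monitoring Committee, but none can be seen in the available text. This also stands, and the point therefore rests on the wording of 9.7.4 against 9.6.3.

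Summarising the last repeat and only listing unscheduled results is a common and stated convention. It need not change if a worst-grade table stands beside it.

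Several stronger readings are tempting, and the documents do not support them:
- A reader might infer that a laboratory abnormality without symptoms would always be rated mild. Section 10.6 tells the investigator to weigh all information about the event, and the grade 3-4 progression rule uses NCI-CTC version 5.0. The severity could differ from the CTC grade; no more can be said.
- A reader might infer that Week 12 laboratory data are left out of the analysis. The 9.7.4 text and the SAP timetable include them. This is a slip in the shells.
- A reader might infer that the new table would supply the laboratory part of the escalation count. That rule applies when three or more of six BIOPIN 6 "subjects at a dose level experience a grade 2 adverse event determined after breaking the code to be an adverse reaction". A worst-grade table carries no attribution.
- A reader might infer that the planned statistics could never separate groups with different numbers of affected subjects. SAP 10.1 also requires the median, and nothing here depends on that argument.

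**Conclusion.** The point holds as a reporting gap. Followed as written, the SAP gives a graded subject count for vital signs and none for laboratory values, without explanation, and its summary rules allow a subject's worst laboratory value to be absent from the summaries in Tables 25-26. No number in the plan changes. The consequence is that one affected subject in a group of six (16.7%) might be visible only in a listing, if the result was superseded by a repeat or fell between visits and was not judged clinically significant.

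The 6.0, 1.2 and 0.5-0.9 values are assumptions chosen to show the mechanism; the documents give no expected rate of such results. The conclusion also assumes that no laboratory grade summary sits in the redacted listings or in the section 11 tables. Because all values are kept and listed, this is a cheap improvement to the report and does not threaten the study's data.

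**What to change.** Add one table to the SAP: number (%) of subjects by worst post-dose CTCAE v5.0 grade, by treatment group, for each chemistry and hematology test that has CTCAE criteria, with a row for any laboratory value of grade 2 or higher. Use all post-dose results: scheduled, repeat, unscheduled and Week 12. The documents do not show that all the listed tests can be graded, or that reference ranges alone are enough, so the SAP should name the tests it grades.

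Correct the shells of Tables 25 and 26 to include Week 12, as 9.7.4 and the timetable already imply. The repeat and unscheduled-visit rules for those two tables can stay. Add a note that the new table describes laboratory safety and does not replace the attributed adverse-reaction count in Protocol 7.8.1.

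If the SAP is closed, produce the table for the study report and document it under Protocol 9.5.3. The cost is a small amount of programming; no new data are needed.
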